Overall Study Duration	12 months
Subject Participation Duration	2 – 5 hours
Single or Multi-Site	Multi site
Objectives	The primary aim of this study is to compare the ease of use and repeatability of AMG vs. EMG neuromuscular responses in surgical settings in which the patients' arm movement is restricted (placed under surgical drapes) in laparoscopic or robotic procedures.
Number of Subjects	105
Diagnosis and Main Inclusion Criteria	Patients undergoing elective robotic or laparoscopic surgery and requiring administration of neuromuscular blocking agents intraoperatively
Study Device	TetraGraph and TOFScan
Duration of Administration	Single stimulation of ulnar nerve repeated at specific intervals as outlined in the Study Procedures (Section 9.2)

4 Introduction

This document is a protocol for a human research study. This study will be carried out in accordance with the applicable United States government regulations and Mayo Clinic research policies and procedures.

4.1 Abstract

Residual neuromuscular blockade is a common complication in the post-anesthesia care unit (PACU) when neuromuscular blocking agents (NMBAs) have been used in the operating room. The only method of reliably detecting residual neuromuscular blockade is through the use of quantitative neuromuscular monitors. Unfortunately, several barriers exist that have prevented the widespread application of these devices, and many practitioners are still using qualitative (subjective) methods (i.e., use a peripheral nerve stimulator) as an assessment of neuromuscular blockade despite the lack of accuracy of subjective methods and the well-described morbidity and mortality associated with residual blockade.

The aim of this study is to determine the usability of two different monitors, the acceleromyography (AMG)-based TOFScan (which relies on muscle movement for measurement of function) and the electromyography (EMG)-based TetraGraph (which relies on measurement of electrical activity) in surgical settings in which access to the arms and hand muscle movements are restricted.

The TetraGraph (Senzime AB, Uppsala, Sweden) is a standalone EMG-based quantitative monitor that received Conformité Européene (CE) and FDA approvals. EMG measures electrical activity within the muscle following peripheral nerve stimulation and is unaffected by involuntary patient motion or restricted muscle movements from surgical positioning. The IntelliVue (Philips, Amsterdam, The Netherlands) is a modular AMG-based monitor that is being used routinely at Mayo Clinic for all surgical procedures in which NMBAs are administered. TOFScan (Draeger Medical Inc., Telford, PA) is another standalone AMG-based quantitative monitor available for routine clinical use in the United States. We plan to compare measurements obtained with Tetragraph and TOFScan monitors during surgical procedures in which the patients' arms are tucked under surgical drapes and access is limited. The comparison will be based on a validated usability scale, the System Usability Scale (SUS) Plus (Table 18.3 and Table 18.4) that was designed to rate the usability of medical devices.

The original System Usability Scale (SUS) was developed by John Brooke in 1986 (https://www.usabilitest.com/system-usability-scale), and it allows investigators to evaluate a wide variety of products and services, including hardware, software, mobile devices and websites. It is a simple, ten-item Likert scale with five response options for respondents; the responses vary from "Strongly agree" to "Strongly disagree." The scale provides a quick and reliable tool for measuring the usability of the product in question.

The usability of the two monitors will be determined throughout various stages of neuromuscular blockade, including onset of blockade following neuromuscular relaxant administration, maintenance, and reversal of blockade with sugammadex or neostigmine until adequate recovery (train-of-four ratio >0.9) is confirmed. At the end of each surgical case, the healthcare provider will be asked to rate the usability of the TetraGraph and the usability of the TOFScan monitors based on the ten items on the SUS scale.

4.2 Background

Neuromuscular blocking agents (NMBAs) are a class of medications routinely used during anesthesia to facilitate endotracheal intubation (1) and improve conditions for optimal surgery (2). However, these medications are also associated with respiratory complications in the early postoperative period due to residual neuromuscular blockade (RNMB) (3-5). Even when neuromuscular blockade is reversed in the operating room, postoperative residual weakness continues to be a common problem in the post-anesthesia care unit (PACU), and a significant number of patients continue to arrive in the PACU with objective evidence of residual neuromuscular blockade (6, 7). While not every patient with residual weakness develops a postoperative complication, many can develop avoidable critical respiratory events (8, 9). Furthermore, special populations such as the elderly are at particular risk for developing complications related to postoperative residual weakness (10). The use of quantitative monitoring has been demonstrated to reliably reduce the incidence of postoperative residual weakness and the ensuing complications (11-13).

Quantitative neuromuscular monitoring devices objectively measure residual weakness and display the results numerically. This is traditionally accomplished by performing a train-of-four (TOF) stimulation at the ulnar nerve and measuring the response of the adductor pollicis muscle. The degree of muscle weakness is determined by calculating the TOF ratio, which consists of the ratio of the fourth muscle contraction to the first. Adequate recovery that excludes clinically significant weakness from neuromuscular blockade is defined as a TOF ratio ≥ 0.9 , a measurement that can be determined reliably only with a quantitative monitor (14, 15). With an abundance of literature supporting the use of objective neuromuscular monitors, a panel of experts recently recommended the universal adoption of such devices whenever NMBA are utilized (16) however, quantitative monitors can be expensive and require additional training.

There are several types of quantitative neuromuscular monitors. These devices can be incorporated into the anesthesia workstation, allowing data to be seamlessly integrated into the electronic medical record. Unfortunately, this setup can preclude using these monitors in the PACU as portability is sacrificed. In contrast, other monitors exist as standalone, portable (handheld) units.

Aside from portability, objective monitors can further be categorized based on the modality utilized to measure responses. Mechanomyography (MMG) measures the force of contraction of the adductor pollicis (thumb) muscle following ulnar nerve stimulation and has served as the traditional "gold-standard". Mechanomyographic responses are precise and reproducible,

however the setup is cumbersome and the lack of commercially available devices has relegated MMG to strictly research purposes. Acceleromyography (AMG) measures acceleration of a muscle group (typically the thumb) in response to stimulation (typically the ulnar nerve). This technique is similar to MMG, but instead of measuring the force of muscle contraction, an accelerometer fixed to the thumb measures the acceleration of the thumb in response to ulnar nerve stimulation. Based on Newton's Second law that states force is proportional to acceleration, the measured acceleration is correlated with the force of contraction in the clinical setting. There are currently two standalone AMG-based monitors available for clinical use: the STIMPOD (Xavant Technologies, Pretoria, South Africa) and the ToFscan (Draeger Medical Inc., Telford, PA). These devices represent improvements in AMG technology over its predecessor, the TOF-Watch (Schering-Plough Corp., Kenilworth, NJ, USA) as they utilize three dimensional transducers that can better quantify the complex motion of the thumb. Despite these advances, the use of AMG can be limited due to patient positioning that precludes free motion of the thumb, as well instances of awakening patients moving their thumb during measurements. Kinemyography (KMG) is based on similar principles to AMG, and relies on the thumb being able to move freely. Upon neurostimulation, KMG utilizes a piezoelectric motion sensor that is bent between the thumb and index fingers following muscle contraction. The degree of this bending is quantified and used to determine a TOF ratio. While Datex-Ohmeda (Helsinki, Finland) manufactures a KMG device that can be incorporated into the anesthesia work station, there are no currently available standalone KMG devices. Electromyography (EMG) devices measure electrical activity, termed compound muscle action potentials (cMAPs) following nerve stimulation (typically at the adductor pollicis muscle after ulnar nerve stimulation). As EMG measures cMAPs and does not require freely moving thumbs for accurate measurements, many experts have referred to this monitoring modality as the "new gold standard". TetraGraph (Senzime AB, Uppsala, Sweden) is a standalone EMG-based device that is FDA-approved. We have previously investigated this device and presented our findings at several annual meetings such as International Anesthesia Research Society (May 2018, May 2017, May 2013), the Society for Technology in Anesthesia (January 2018), and the American Society of Anesthesiologists (October 2017, October 2012), European Society of Anaesthesiology (June 2018, June 2015) (17). Furthermore, we have recently submitted abstracts to the PostGraduate Assembly in Anesthesiology in December 2018 as well as a manuscript describing a multicenter, volunteer study investigating TetraGraph versus AMG-based monitors. Our work thus far has found this device to be easy to apply, reliable, and able to provide comparable measurements to other quantitative monitors.

Many clinicians default to the antiquated practice of subjective monitoring (18, 19), which refers to visual or tactile evaluation of the train-of-four (TOF) in response to neurostimulation provided by peripheral nerve stimulation. However, subjective evaluation may provide inaccurate information and assessment of full recovery compared to objective evaluation (20, 21). A consensus statement by the international panel of experts in neuromuscular blockade issued in 2018 state that subjective evaluation is not predictive of adequate neuromuscular recovery, and is not sensitive to the presence of residual weakness. They state that their use should be abandoned

in favor of objective monitoring, because after the TOFR recovers to >0.40, anesthesia providers can no longer detect the presence of fade by subjective evaluation and they may assume a complete recovery from neuromuscular blockade, despite the presence of minimal levels of NMB(16). It is worth highlighting that after tracheal extubation, even minimal degrees of residual block is associated with impaired function of respiratory and pharyngeal muscles, upper airway obstruction (22),hypoxemia (23), and awareness during anesthesia (24)

Utilizing recommendations from the Good Clinical Practice (GCP) Guidelines for monitoring of neuromuscular function (25), we will compare acceleromyographic and electromyographic responses to train-of-four stimulation of the ulnar nerve in surgical settings where the arm movement is restricted by the surgical drapes (such as laparoscopic and robotic surgery). The time points of interest will include the onset of blockade following neuromuscular relaxant administration, maintenance of block, and reversal of blockade with sugammadex or neostigmine until adequate recovery (train-of-four ratio >0.9). The reliability of the two monitors will be evaluated post hoc by comparing the repeatability of responses, and the usability of the two monitors will be evaluated by the healthcare providers using the System Usability Scale (SUS) Plus scale, a simple, 10-item Likert scale with 5 response options for the evaluators (https://www.usabilitest.com/system-usability-scale).

4.3 Risks and Benefits

- The benefits of using neuromuscular blockade monitoring devices:
 Early detection of optimal time for tracheal extubation; optimal management of intraoperative depth of neuromuscular block to facilitate surgical procedures; determination of appropriate time and dose of sugammadex reversal; and detection of residual neuromuscular blockade. This is currently the standard of care practice at Mayo Clinic.
- The risks of using neuromuscular blockade monitoring devices: Slight discomfort when electrical stimulation is administered in awake volunteers; however, our patients will be anesthetized, rendering this risk as extremely minor.

5 Study Objectives

Primary Objective

Compare the objective EMG-derived data using TetraGraph (TOFR, TOFC, PTC) with those obtained from the AMG-based TOFScan monitor and assess the reliability and usability of the two objective monitors.

Secondary Objective

Determine the incidence of failure to calibrate and monitor neuromuscular responses using the two monitors.

6 Study Design

6.1 General Description

[figure not shown]
This unblinded, multi center, prospective, randomized, observational study will involve 35 patients undergoing surgical procedure that involved administration of neuromuscular blockade agents intraoperatively in surgical settings in which the patients' arms are placed under surgical drapes and are unavailable to the anesthesiologist. These surgical procedures include laparoscopic and robotic surgeries.

6.2 Number of Subjects

One hundred five (105)

6.3 Duration of Participation

2-5 hours, depending on duration of surgery

6.4 Primary Study Endpoints

The primary endpoint of the study will be to determine the usability of the two monitors using the SUS Plus scale.

6.5 Secondary Study Endpoints

The secondary endpoint is to determine the reliability of the two monitors, by comparing the frequency of each monitor's failure to calibrate and measure evoked responses.

6.6 Identification of Source Data

The study data points will be recorded on the developed Case Report Forms (CRFs) by the study team members. In addition to the data collected intraoperatively, several intraoperative characteristics will also be extracted from the medical record (Table 18.2). These will include type and total dose of NMBA used, time and dose of last NMBA administration, time and dose of specific reversal agent administration, time of tracheal extubation, and TOF ratio at the time of extubation (if available).

7 Subject Selection Enrollment and Withdrawal

7.1 Inclusion Criteria

- Age > or = 18 years old
- Patients willing to participate and provide an informed consent
- Patients undergoing an elective laparoscopic or robotic surgical procedure that requires use of NMBA agents administered intraoperatively.

7.2 Exclusion Criteria

- Patients with disorders, such as stroke, carpal tunnel syndrome, broken wrist with nerve damage, Dupuytren contracture, or any similar wrist injury.
- Patients with systemic neuromuscular diseases such as myasthenia gravis
- Patients with significant organ dysfunction that can significantly affect pharmacokinetics of neuromuscular blocking and reversal agents, i.e., severe renal impairment or end-stage liver disease.
- Patients having surgery that would involve prepping the arm or leg into the sterile field

7.3 Subject Recruitment, Enrollment and Screening

On a daily basis, there are over 20 elective surgical cases performed at Mayo Clinic in Florida and thus no difficulties in accrual are anticipated based on historical volumes. We will target at least 3 participants per week to complete this study. The initial accrual period will last at least 3 months followed by interim analysis and additional time for accrual will be determined to meet the target. Patients will be provided with a Research Participant Consent and Privacy

Authorization Form describing the study devices, protocol, inclusion and exclusion criteria, as well as risks and benefits of participation.

7.4 Early Withdrawal of Subjects

7.4.1 When and How to Withdraw Subjects

Patients are free to withdraw at any time and for whatever reason. If patient withdraws consent prior to arrival to operating room, the study data will not be collected. If patient withdraws consent after study data was already completed, the participant will need to provide instructions to the study team to remove his/her data from the data set. Pre-specified reasons for discontinuing include, but are not limited to, the following:

- Patient Request: Patient decided that he/she did not want to continue (for any reason)
- Adverse Event: Patient experienced a related or unrelated event that would interfere with the study objectives/evaluation
- Inclusion/Exclusion Discrepancy/Violation: Patient should not have been enrolled
- Other: Any other reason

7.4.2 Data Collection and Follow-up for Withdrawn Subjects

If a Participant withdraws from the study, no additional attempts will be made to contact the Participant.

8 Study Device

8.1 Description

TetraGraph (Figure 19.1) device is a FDA approved neuromuscular transmission monitor capable of measuring the depth of neuromuscular block in anesthetized patients who received neuromuscular blocking agents. TetraGraph uses EMG to measure the muscle action potentials that are generated in response to electrical neurostimulation via skin (ECG) electrodes. TetraGraph data is recorded on the monitor's built-in SD card, and all intraoperative data will be recorded and later downloaded for purposes of analysis. The recorded data do not contain PHI, only the date/time of recording, and any additional intraoperative interventions, such as the time of NMBA dose administration, time of antidote administration, time of extubation, etc. These events are flagged in the monitor's integrated SD card recordings.

TetraGraph uses EMG to measure the muscle action potentials that are generated in response to percutaneous electrical neurostimulation, and is not subject to the limitations imposed by the AMG-based monitors: the measurement of the electrical compound muscle action potentials (cMAPs) can be made even when the thumb movement is restricted.

The TOFScan (Figure 19.2) is a neuromuscular transmission monitor that is based on AMG technology, and is used routinely in clinical care at Mayo Clinic. It can measure and record the evoked responses (acceleration) of the hand muscle adductor pollicis (thumb) and calculate the degree of neuromuscular block (the TOF ratio).

8.2 Method for Assigning Subjects to Treatment Groups

This is an open-label investigation and all study participants are assigned to both TetraGraph and TOFScan devices. The randomization involves the use of dominant vs non-dominant arm for the placement of TetraGraph device.

The randomization will be performed utilizing REDCap and assigned anesthesia clinical care team will be informed of patients' assigned to guide them with the selection of the assigned treatment option.

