9.2 Visit 2 (Randomization and Treatment – day of surgery)

- Elective surgical procedure as in which intraoperative access to the arms is restricted because of surgical draping.
- Anesthetic management will be standardized to utilize rocuronium, sevoflurane, and sugammadex or neostigmine at the discretion of the attending anesthesiologist
- Prior to induction of anesthesia, the Tetragraph electrodes will be placed over the ulnar nerve and the thumb to measure the response of adductor pollis nerve. Randomization will be performed utilizing REDCap and involves the use of dominant vs non-dominant arm.

• Following induction of anesthesia but prior to NMBA administration, baseline values will be recorded from both monitors after calibration.

- Anesthesia providers will have access to the TetraGraph and TOFScan values during the
 entire procedure, and will make clinical decisions as per usual clinical routine at Mayo
 Clinic.
- After NMBA administration, sets of measurements will be taken with the two monitors at regular intervals (every 12 sec, 20 sec, 1 min, 15 min, etc.) as required per usual clinical routine and determined by the anesthesia attending.
- Near the conclusion of the operation but prior to the reversal of neuromuscular block, another set of measurements will be taken, with the two monitors, as per usual clinical routine, in order to determine the appropriate reversal drug dosage.
- After sugammadex or neostigmine administration, measurements will be taken every 20 seconds until return of neuromuscular function is documented.
- Following documentation of adequate neuromuscular function (TOF ratio is >0.9,) the devices will be removed and the patient will proceed along the standard recovery pathway.

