10.1 Sample Size Determination

Based on paired t-test, 23 enrolled patients will give 90% power to detect a difference in TOF ratios with a significance level of 0.05 (JMP Pro Software version 13.0.0

[August 23, 2018]; SAS Institute Inc., Cary, NC). We utilized a standard deviation of 0.07 that was determined during our multi-center volunteer study comparing another AMG device and TetraGraph. However, each participating center will enroll 35 patients to take into account

patient loss or missing data. The total number of patients for this study from all 3 centers will be aimed at 105 participants.

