10.2 Statistical Methods

10.2.1 Descriptive Statistics

Analysis of agreement between the two monitors will be assessed using Bland-Altman. The limits of agreement are defined as bias \pm 2 SD, where SD denotes the standard deviations of the differences. Limits of agreement are interpreted as the reference range within which 95% of the differences will lie. The bias and the limits of agreements surrounding the bias (\pm 2 SD) will be calculated with 95% confidence intervals. Statistical significance will be defined as a p-value <0.05. Comparison of the usability of the two monitors will be made using the System Usability Scale (SUS) Plus. The SUS is particularly relevant to user experience when comparing two monitors that are based on different technologies (AMG and EMG). It will allow us to make a comparison of the two monitors in a surgical setting in which access to the monitoring muscle site (the thumb and hand) is limited. Because SUS is technology-neutral, we will be able to continue to use it in usability testing as technology evolves over the years, allowing us to continually evaluate and select the optimal monitoring technology available.

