18.2 Intraoperative Data

•		Date of Surgery (dd / mm / yyyy):		Examiner's Initials:		
Wrist circumference (right):		Wrist circumference (left):		Dominant side: L / R		
Ankle circumference (right):		Ankle circumference (left):				
Age (yrs):	Weight	(kg):		Height (cm):		BMI:
Muscle relaxant name	:					
Muscle relaxant total dose (mg):						
Time of first muscle re	elaxant	dose (mm :	: hh):		:	am / pm

Reversal agent name:					
Reversal agent dose (mg)	:				
Time of reversal agent administration (mm : hh):				:	am / pm
Time of extubation:		:		am / pm	

TetraGraph (TG) / TOFScan

	Time	TetraGraph (TG) Arm L/R	TOFScan Arm L / R	TOFR # 3 (if needed)
Calibrated baseline TOFR and supramax current				
TOFC=0 (post initial dose of NMBA)				
Time Interval (first recheck)				
Time Interval (second recheck)				
Time Interval				
Time Interval				
Time Interval				

Time Interval		
Time Interval		

Time Interval		
pre-SGX		
+60sec after SGX		
+120 sec after SGX		
+180 sec after SGX		
+260 sec after SGX		
Extubation		
Time to recovery following SGX (TOFR ≥0.9)		
T0 (on arrival to PACU)		
T5 (5 min after PACU arrival)		
T10 (10 min after PACU arrival)		

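### The TOF-ratio agreement analysis in 10.2.1 does not use the randomised arm, so the confidence interval of the bias may be wider than it needs to be

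*Combined protocol and SAP*

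**What the plan says.** All patients wear both monitors. Section 8.2 describes the only randomised factor: "The randomization involves the use of dominant vs non-dominant arm for the placement of TetraGraph device". It does not say where the TOFScan goes, nor does it give the allocation ratio or any blocking. The CRF in 18.2 has a dominant-side field and a separate side field for each device, including "TOFScan Arm L / R". This implies opposite arms without stating it.

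Section 10.2.1 plans a Bland-Altman analysis with limits at bias ± 2 SD, "where SD denotes the standard deviations of the differences", and 95% CIs for the bias and the limits. It adds: "Limits of agreement are interpreted as the reference range within which 95% of the differences will lie". It has no term for arm and does not say whether ratios are raw or baseline-corrected.

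On baseline, 9.2 states that before the blocking agent is given "baseline values will be recorded from both monitors after calibration", and 18.2 has a row for "Calibrated baseline TOFR and supramax current". No analysis section refers to either. The only sensitivity analysis in the plan is the exclusion of withdrawn patients (10.3).

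**The concern.** A trial that randomises a single factor would normally say how the analysis uses it. Suppose the two devices are on opposite arms and the dominant hand responds differently. Each patient's difference between devices then moves up or down by some amount h according to the assigned arm. Part of the scatter of the differences has a known, randomised cause, and a plain Bland-Altman calculation treats it as noise when it forms the CI of the bias.

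The TOF-ratio comparison is part of the primary objective (section 5) and is what the sample size rests on (10.1). At stake is the precision of the estimated bias.

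A smaller, related gap concerns baseline. Randomising the arm cannot remove an offset between the devices that exists before any block. The plan collects paired baselines but does not say that it will report them, so a reader could not tell such an offset from disagreement during block and recovery.

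**Working it through.** **Inputs from the documents.** N = 105 (6.2, 10.1). SD = 0.07, from 10.1: "We utilized a standard deviation of 0.07 that was determined during our multi-center volunteer study comparing another AMG device and TetraGraph". The text does not say that this is the SD of paired differences; that is assumed here.

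**The plan's own figure.** Section 10.1 gives 23 patients for 90% power at 0.05 by a paired t-test, but states no difference to detect, so 23 cannot be reproduced from the text alone. Solving backwards (two-sided, noncentral t) gives 0.7075 × 0.07 = 0.0495. With a difference of 0.05 the formula returns n = 23, with power 90.5%. 3 × 35 = 105 is correct.

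**Assumptions.** The TOFScan is on the opposite arm, allocation is 1:1, and the within-arm SD is 0.07. The hand effect shifts a patient's difference by +h or −h, so the two arm groups differ by 2h. The documents give no h; 0.01, 0.03 and 0.05 are shown as a range.

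**CI of the bias, one difference per patient.**
- Without the arm: SE = √(0.07² + h²)/√105.
- With the arm: SE = 0.07/√105 = 0.0068.

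| h | SE without arm | 95% half-width (1.96 × SE) without → with arm | CI narrower by |
|---|---|---|---|
| 0.01 | 0.0069 | 0.0135 → 0.0134 | 1% |
| 0.03 | 0.0074 | 0.0146 → 0.0134 | 8% |
| 0.05 | 0.0084 | 0.0165 → 0.0134 | 19% |

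**Repeated readings.** Table 18.2 has about 20 time rows per patient. With m readings and within-patient correlation r, SE² = (0.07² × (r + (1 − r)/m) + k²h²)/105, where k is the share of readings in which h acts. Take m = 10 and r = 0.5, both assumed:
- h in every reading (k = 1): SE falls from 0.00585 to 0.00507 at h = 0.03 (13%) and from 0.00703 to 0.00507 at h = 0.05 (28%).
- h in half the readings (k = 0.5): the gain is 4% and 10%.

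**Limits of agreement.** Limits at ± 2 total SD cover 95.5%, 95.5% and 95.9% of the differences for h = 0.01, 0.03 and 0.05. Limits cut to the within-arm SD would cover 95.2%, 93.4% and 89.7%. The pooled limits meet the definition in 10.2.1; the narrowed ones fall short of it at the two larger values.

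**Baseline break-even.** With a t quantile on 104 degrees of freedom, the half-width is 1.983 × 0.07/√105 = 0.0135. If an offset acts in proportion to the ratio (assumed), it shifts the raw bias at a ratio of 0.90 by 0.90 × offset. The shift equals the half-width when the offset is 0.0135/0.90 = 1.5%. At lower ratios the shift is smaller.

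**Noise from correction.** With no true offset and a baseline error SD e per device, the SD at 0.90 becomes √(0.07² + 2 × (0.9e)²): 0.071, 0.074 and 0.080 for assumed e = 0.01, 0.02 and 0.03.

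**The case against.** The strongest reply is that no wrong result follows. The half-width falls by only 0.0001, 0.0012 or 0.0031, against limits of about ± 0.14 and an implied detectable difference of about 0.05. The trial enrols 105 where 23 were calculated, so precision is not scarce. If allocation is blocked, h cancels in the mean and the unadjusted CI merely errs on the safe side: it covers 95.2% to 98.4% over the same range of h. The largest h is as big as the implied device difference, and nothing in the documents supports it. All of this stands, and it is why the point is a free improvement and not a flaw in validity.

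A reader might infer more, in three ways:
- **That the bias is confounded with hand, or that the limits are inflated and should be narrowed.** Under 1:1 allocation the expected bias is unaffected. By the plan's own definition the limits must hold arm variation.
- **That repeated readings make the gain much larger.** That needs h to be the same at every reading. The readings run from complete block to recovery, and no section shows a constant effect.
- **That raw ratios are the wrong thing to analyse.** The documents report no baseline offset and do not say whether the displayed ratios are already baseline-corrected. Section 9.2 says "Anesthesia providers will have access to the TetraGraph and TOFScan values", so raw agreement is the relevant main result. The paired baseline difference would show any offset more simply than a corrected analysis.

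**Conclusion.** The point holds as a modest loss of precision. Section 10.2.1 leaves out the only randomised factor. If the devices are on opposite arms, the CI of the TOF-ratio bias may be 1% to 19% wider than it need be, expressed as the narrowing available for h from 0.01 to 0.05. This rests on 0.07 being the within-arm SD of paired differences, on one difference per patient, and on hand effects that are assumed. If the TOFScan shares the arm, the arm term brings no such gain.

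The baseline part is secondary. The 1.5% figure is a break-even at one ratio, not evidence that an offset exists. The expected bias, the definition of the limits, the SUS endpoint (6.4) and N are not affected.

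**What to change.** In 10.2.1, for TOF ratio only:

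1. Estimate the bias and its 95% CI from a mixed model of the paired differences, with assigned arm as a fixed effect and patient as a random effect. Report the equally weighted mean of the two arm groups. Take the assigned arm from the REDCap randomisation record; the CRF gives the arm actually used.
2. Keep the limits at bias ± 2 total SD, with arm variation left in the SD. Take their 95% CIs from a bootstrap that resamples patients.

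In 8.2, state whether the TOFScan goes on the opposite arm.

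Optional: keep raw agreement as the main result and report the paired baseline difference between the devices. Add one sensitivity analysis, in patients with both baselines, in which each ratio is divided by that device's own baseline. First confirm that the displayed ratios are not already corrected, and note that correction may add noise.

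The cost is SAP wording and one sentence in 8.2. No new data are needed. The arm term uses one degree of freedom, and the model and bootstrap take slightly more work than a plain Bland-Altman calculation.
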